## 11 STATISTICAL PLAN

The statistician for this study is [name].

### 11.1 STATISTICAL ANALYSIS STRATEGIES

To help ensure reproducible results, these a priori plans specify the planned analyses for each specific aim along with guidelines for sensitivity analyses performed to assess the robustness of the major results to reasonable perturbations of the assumptions, choices, and methods used. The plans also include 1) secondary analyses as an aid for understanding and interpreting the main analysis results, 2) a role for exploratory analyses for hypothesis generation, and (3) necessary descriptive graphical and tabular methods used to visualize the data, examine relationships among variables, and characterize the participants.

Immediately before and after a 10-min tDCS treatment is applied, TMS pulses at 120% of RMT intensity will be applied for 10 minutes at a frequency of 0.25Hz. For each of those 75 TMS pulses, the MEP amplitude will be measured by EMG in the ADM muscle. Thus, we will have 75 MEP amplitudes before and after each of the 3 tDCS conditions is applied. (In total, each subject contributes 450 MEP amplitudes.) For each set of 75 amplitudes, we will compute the average amplitude. The change in average amplitude ( $\Delta A_{ij}$ ) will be computed as the post-tDCS average minus the pre-tDCS average:  $\Delta A_{ij^*} = A_{ij^*}(post) - A_{ij^*}(pre)$  for the  $i^{th}$  subject and the  $j^{th}$  tDCS condition. The primary analysis will focus on these changes in average amplitude and will rely on a linear mixed-effects model which assumes a compound-symmetry covariance matrix; in other words, a repeated-measures ANOVA model. The dependent variable will be the change in average amplitude ( $\Delta A_{ij^*}$ ) and the explanatory variables will be tDCS treatment condition, treatment period, sequence group ( $v$ ), and indicator variables representing carryover effects ( $\lambda$ ).

Entry is the expected value of $\Delta A_{ij^*}$ in the target population	Period 1	Period 2	Period 3
Sequence ACS	$\mu_A + v_1 + p_1$	$\mu_C + v_1 + p_2 + \lambda_A$	$\mu_S + v_1 + p_3 + \lambda_C$
Sequence ASC	$\mu_A + v_2 + p_1$	$\mu_S + v_2 + p_2 + \lambda_A$	$\mu_C + v_2 + p_3 + \lambda_S$
Sequence CAS	$\mu_C + v_3 + p_1$	$\mu_A + v_3 + p_2 + \lambda_C$	$\mu_S + v_3 + p_3 + \lambda_A$
Sequence CSA	$\mu_C + v_4 + p_1$	$\mu_S + v_4 + p_2 + \lambda_C$	$\mu_A + v_4 + p_3 + \lambda_S$
Sequence SAC	$\mu_S + v_5 + p_1$	$\mu_A + v_5 + p_2 + \lambda_S$	$\mu_C + v_5 + p_3 + \lambda_A$
Sequence SCA	$\mu_S + v_6 + p_1$	$\mu_C + v_6 + p_2 + \lambda_S$	$\mu_A + v_6 + p_3 + \lambda_C$

Note: We define  $v_6 = (-1) * (v_1 + v_2 + v_3 + v_4 + v_5)$  and  $p_3 = (-1) * (p_1 + p_2)$

The fitted model will be used to tabulate statistical estimates (all with 95% confidence intervals) of the parameters of interest: variance components, intra-class correlations, direct effects of tDCS ( $\mu$ ), period effects ( $p$ ), sequence-group effects ( $v$ ), and first-order carryover effects of tDCS ( $\lambda$ ). We will assume that there are no differential second-order carryover effects. The fitted model will also be used to test the main hypothesis,  $H_o: "(\mu_A - \mu_S) = 0 = (\mu_A - \mu_S)"$ , using an F-test of size  $\alpha = 0.05$ . If (and only if) this null hypothesis is rejected, then (and only then) we will test the two component sub-hypotheses using F-tests of size  $\alpha=0.05$ :  $H_{oA} (\mu_A - \mu_S)=0"$ ,  $H_{oC} "(\mu_C - \mu_S) = 0"$ .

We will also perform an equivalence test in which equivalence is defined as a difference of less than  $0.1mV$  (i.e., tolerance  $T = 0.1mV$ ). The null hypothesis that the anode and cathode stimulation are not equivalent is  $H_0 = "|\mu_A - \mu_C| > T = 0.1mV"$ . The null hypothesis will be rejected if the 95% confidence interval for  $(\mu_A - \mu_C)$  lies entirely within the interval  $[-T, T]$ .

All hypothesis tests that are observed to be NOT statistically significant will be reported as being inconclusive. Hypothesis tests that are not statistically significant are entirely inconclusive and no conclusions can be drawn from those tests. Every statistical test procedure is (by definition) incapable of establishing that the null hypothesis is true. The word "inconclusive" will be used when reporting a test that was not statistically significant. To avoid over-reliance on p-values, the focus of the analyses will be on point-estimates and interval-estimates of the magnitudes of the population parameters of interest (e.g, effects, correlations, variance components.)

In secondary analyses, time-specific changes in amplitude will be computed as  $\Delta A_{ijT} = A_{ijT}(post) - A_{ijT}(pre)$  for  $T = 1, 2, 3, \dots, 75$ . Graphical descriptive statistical methods will be used to visualize and summarize the temporal trajectories of MEP amplitudes.

Sensitivity analyses will be used to evaluate the robustness of the main results to reasonable perturbations of the methods and assumptions used. This set of analyses will examine goodness of fit diagnostics for the linear model, and will include modified versions of the main analyses; e.g., omission of period effects or sequence effects or carryover effects.

For Aim 3, parameter estimates needed for planning a future study will be tabulated along with their 95% confidence intervals. In planning the future study it will be critically important to take into account the levels of uncertainty about the parameter estimates as indicated by the confidence intervals.

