### 2.3.1 SPECIFIC AIMS

Aim 1. For each tDCS condition, estimate mean changes in TEP and MEP amplitudes induced by tDCS stimulation.

Aim 2. Compare the three tDCS conditions (anode, cathode, sham) in terms of the mean changes in TEP and MEP amplitude.

Aim 3. Obtain statistical estimates of variance components needed for the planning of a future study.

---

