### 2.3.2 RESEARCH HYPOTHESES

We hypothesize that anodal and cathodal tDCS stimulation increases and decreases TEP and MEP amplitudes compare to sham tDCS condition, respectively. We further hypothesize that TEP and MEP amplitudes are positively correlated.

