#### 4.1 TREATMENT ASSIGNMENT PROCEDURES

Each participant will experience all three versions of tDCS (anode, cathode, sham). There are 6 ways to order the three tDCS treatments: ACS, ASC, CAS, CSA, SAC, SCA. By randomization, each participant will be assigned to one of these sequences. Three participants will be assigned to each of these 6 sequence groups. (The 6 sequences comprise two Latin squares). Each session has 1-day gap to remove outlasting effects. The randomization schedule will be computed prior to recruitment of subjects and the random assignments will be concealed from the personnel who screen potential participants until the moment that the participant is enrolled and ready for baseline evaluations. To accomplish this, the randomization schedule will be used to create a set of sequentially-numbered opaque sealed envelopes (SNOES).

ACS: Anode → Cathode → Sham (3 participants)

ASC: Anode → Sham → Cathode (3 participants)

CAS: Cathode → Anode → Sham (3 participants)

CSA: Cathode → Sham → Anode (3 participants)

SAC: Sham → Anode → Cathode (3 participants)

SCA: Sham → Cathode → Anode (3 participants)

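### The primary crossover model sets no constraint on the carryover terms, so the condition means, period effects and carryover effects it promises to tabulate are not identified

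*Combined protocol and SAP*

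**What the plan says.** Section 11.1 (Statistical Analysis Strategies) models each participant's change in average MEP amplitude with terms for tDCS condition, period, sequence group and "indicator variables representing carryover effects". A table gives the expected change in each of the 18 sequence-by-period cells. Every period 1 cell is μ + v + p. Every period 2 and period 3 cell adds exactly one λ, belonging to the condition given in the preceding period. All three of λ_A, λ_C and λ_S appear.

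The note under the table defines v_6 and p_3 so that the v terms and the p terms each sum to zero. It does not mention λ, and no reference level for λ is named elsewhere. The only further statement on carryover is that differential second-order effects are assumed absent.

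The plan then commits itself: "The fitted model will be used to tabulate statistical estimates (all with 95% confidence intervals) of the parameters of interest". That list names μ, p, v and λ, and describes μ as the "direct effects of tDCS". The same section says that "the focus of the analyses will be on point-estimates and interval-estimates of the magnitudes of the population parameters of interest". Aim 1 in section 2.3.1 reads: "For each tDCS condition, estimate mean changes in TEP and MEP amplitudes induced by tDCS stimulation".

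**The concern.** The three carryover indicators add up to an indicator for being in period 2 or 3, and the condition and period terms already span that indicator. With v and p constrained and λ left free, the model has one redundant parameter. Average carryover cannot be separated from the contrast of period 1 with the later periods, and through the sum-to-zero rule on p it also passes into the level of every μ.

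At stake is the main descriptive output of a pilot that says it puts estimation ahead of p-values. Two analysts could fit the stated model correctly, apply different software defaults for λ, and report different condition means, period effects and carryover effects, each with different intervals. If the constraint is not fixed in advance, it can also be chosen after the results are seen.

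**Working it through.** **Inputs** (sections 4.1 and 11.1): six sequences, three participants per sequence, three periods, so 54 change scores; the cell means in the table; the two constraints in the note. The plan states no parameter count or rank, so there is no figure of its own to reproduce.

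**Parameter count.** 3 (μ) + 5 (free v) + 2 (free p) + 3 (λ) = 13.

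**Rank.** The 54 × 13 design matrix built from the table has rank 12. The 18 × 13 matrix of cell means gives the same rank. There is one null direction.

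**The null direction.** For any constant c, add c to every λ, subtract 2c/3 from every μ, add 2c/3 to p_1, subtract c/3 from p_2 and from p_3, and leave v alone. The p terms still sum to zero: 2c/3 − c/3 − c/3 = 0. The change in each cell mean is:

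- period 1 (μ + v + p_1): −2c/3 + 0 + 2c/3 = 0
- period 2 (μ + v + p_2 + λ): −2c/3 + 0 − c/3 + c = 0
- period 3 (μ + v + p_3 + λ): −2c/3 + 0 − c/3 + c = 0

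**Illustration with invented values (mV), c = 0.3, all v = 0.** The two parameter sets below give the same mean in all 18 cells.

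| | μ_A, μ_C, μ_S | p_1, p_2, p_3 | λ_A, λ_C, λ_S |
|---|---|---|---|
| Set 1 | 0.30, −0.20, 0.00 | 0.05, −0.02, −0.03 | 0.1, −0.1, 0.0 |
| Set 2 | 0.10, −0.40, −0.20 | 0.25, −0.12, −0.13 | 0.4, 0.2, 0.3 |

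For example, sequence ACS in period 2 is μ_C + p_2 + λ_A. Set 1 gives −0.20 − 0.02 + 0.1 = −0.12, and set 2 gives −0.40 − 0.12 + 0.4 = −0.12. The sham mean change is 0.00 in one set and −0.20 in the other, while μ_A − μ_S is 0.30 in both.

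**What is estimable.** A linear combination is estimable only if the null direction leaves it unchanged.

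- Not estimable: each μ, each p, each λ, and p_1 − p_2.
- Estimable: every v, every difference between μ's, every difference between λ's, p_2 − p_3, and μ_j + (2/9)(λ_A + λ_C + λ_S).

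**Sensitivity fits named in section 11.1.** Without carryover: 10 parameters, rank 10. Without period: 11 parameters, rank 11. Without sequence: 8 parameters, rank 7, so μ is still not identified.

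**Size.** The plan names no λ constraint, so two natural ones are compared here. Under sum-to-zero, the fitted μ_j estimates μ_j + (2/9)(λ_A + λ_C + λ_S). Under λ_S = 0 it estimates μ_j + (2/3)λ_S. The gap is (2/9)(λ_A + λ_C − 2λ_S), the same for all three conditions. It is zero in expectation if carryover does not differ by condition, but not zero in a given sample. Generalised least squares under compound symmetry, with the total variance of a change score set to 1 and the correlation treated as known, gives:

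| Assumed correlation | 0 | 0.3 | 0.5 | 0.7 | 0.9 |
|---|---|---|---|---|---|
| SE of μ_S, sum-to-zero | 0.255 | 0.249 | 0.245 | 0.242 | 0.238 |
| SE of μ_S, λ_S = 0 | 0.373 | 0.337 | 0.312 | 0.284 | 0.253 |
| Ratio of the two SEs | 1.464 | 1.355 | 1.271 | 1.175 | 1.064 |
| Sampling SD of the gap in μ | 0.192 | 0.161 | 0.136 | 0.105 | 0.061 |

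Relative to the sum-to-zero SE, the gap has an SD of 0.061/0.238 = 26% to 0.192/0.255, about 76%. The SE of μ_A − μ_S is the same whether λ sums to zero or any one of the three λ's is set to zero.

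**The case against.** - **Narrow reach.** Every formal test uses differences between conditions, and those are estimable. The polarity hypothesis, that stimulation "increases and decreases TEP and MEP amplitudes compare to sham tDCS condition", is about contrasts with sham. Variance components, which matter most for Aim 3, do not depend on the constraint either. All of this stands, and it is why the point does not threaten the main test.
- **Aim 1 need not use the raw coefficient.** Condition means can be estimated once defined, and the plan foresees descriptive tables. That is true, but section 11.1 lists μ itself for tabulation and defines no adjusted mean. Defining one would settle Aim 1 and still leave p and λ unidentified.
- **Carryover may be negligible.** Section 4.1 says "Each session has 1-day gap to remove outlasting effects", and the sensitivity analyses include "omission of period effects or sequence effects or carryover effects". The first is an intention about the design; the primary model still fits λ and promises intervals for it. Of the second, the fits without carryover or without period identify μ, but neither is the primary model, and the fit without sequence effects has the same defect.
- **Indicator variables imply a reference level.** None is named, and the table carries all three λ's.
- **The choice of constraint belongs to the trial statistician.** This stands in part: any constraint stated in advance removes the ambiguity. Setting λ_S = 0 would keep the direct-effect reading of μ, but only by assuming that sham leaves no carryover. This design cannot test that, because only differences between λ's are estimable.

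**Conclusion.** The concern holds. The model as written has one parameter more than its rank. The plan therefore promises estimates and 95% intervals for individual μ, p and λ values that the stated model does not define; of the fixed effects it lists, only v is identified. The rank result is exact and needs no assumption.

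The consequence is limited to the table of estimates and to Aim 1. The F-tests, the equivalence test, Aim 2 and the variance components are sound in this respect. The size figures rest on assumed correlations and on one chosen pair of constraints. They show that two different estimands give different answers, not that either is biased or less precise. No effect in mV can be given, because the documents state neither an SD nor a carryover size. This should be corrected before analysis, but it does not undermine the main comparison.

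**What to change.** Add λ_A + λ_C + λ_S = 0 to the note under the table in section 11.1, in line with the convention already used there for v and p. Then state three things:

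1. μ_j is the model-adjusted mean change for condition j averaged over the three periods. In terms of the unconstrained model it equals μ_j + (2/9)(λ_A + λ_C + λ_S). It includes two thirds of the mean carryover, so it should not be labelled a direct effect free of carryover.
2. The period effects also absorb average carryover.
3. Each tabulated λ is a deviation from the mean carryover, so only differences between conditions are interpretable.

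If the statistician prefers another constraint, such as λ_S = 0, the plan should state it, give the assumption behind it and say what μ then means. The sensitivity fit without sequence effects needs the same constraint.

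The cost is one constraint and two or three sentences. No treatment contrast, test, power or variance component changes, and no extra data are needed.

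### The main null hypothesis states anode minus sham twice and omits cathode minus sham, so the gate as written ignores the cathodal effect

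*Combined protocol and SAP*

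**What the plan says.** The primary analysis in section 11.1 fits a "linear mixed-effects model which assumes a compound-symmetry covariance matrix" to the change in average MEP amplitude, with terms for condition, period, sequence and carryover. The main hypothesis is then tested by an F-test of size 0.05. Its null is printed as "\mu_A - \mu_S) = 0 = (\mu_A - \mu_S" (the outermost brackets fall outside the quotation).

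The next sentence makes this test a strict gate: "If (and only if) this null hypothesis is rejected, then (and only then) we will test the two component sub-hypotheses". Those two are H_oA, anode equals sham, and H_oC, cathode equals sham, each tested at 0.05. H_oC is printed correctly.

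Two other places show what the test is meant to serve:

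- Section 2.3.1, Aim 2: "Compare the three tDCS conditions (anode, cathode, sham) in terms of the mean changes in TEP and MEP amplitude".
- Section 2.3.2: "We hypothesize that anodal and cathodal tDCS stimulation increases and decreases TEP and MEP amplitudes compare to sham tDCS condition, respectively".

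No other part of the document restates the main null, and the numerator degrees of freedom of the gate test are not given.

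**The concern.** Both halves of the printed null are the same contrast. A null with two components, one of them cathode versus sham, cannot be the null that is printed. Numerator degrees of freedom are not stated, so the formula alone defines the gate.

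An analyst who codes it literally tests anode versus sham, and on rejection tests anode versus sham again together with cathode versus sham. Cathode versus sham could then be tested only after a significant anodal result, however strong the cathodal effect. That puts at risk the formal test of the cathodal part of the MEP hypothesis.

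There is a second, smaller risk. If the slip is noticed only once results are known, someone must choose between the printed gate and the intended one with the data in view.

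**Working it through.** **Inputs from the documents.** 18 participants (section 3). Six sequences with three participants each (section 4.1). Three periods, hence 54 change scores. Model terms, gate rule and α = 0.05 (section 11.1). Section 11.2 rests the sample size on expert opinion and gives no effect size or SD, so effects below are assumptions, expressed in within-subject SDs (σ) of the change score. Complete data are assumed.

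**Step 1: rank of the null.** On (μA, μC, μS), the printed null has rows (1, 0, −1) and (1, 0, −1), which is rank 1. The intended null has rows (1, 0, −1) and (0, 1, −1), which is rank 2. The printed gate is therefore the same test as H_oA.

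**Step 2: precision.** With 18 subject effects (which absorb sequence), 2 period, 2 treatment and 2 first-order carryover terms, the design has rank 18 + 2 + 2 + 2 = 24. Residual df are 54 − 24 = 30. Each active–sham contrast has variance v = 5/36 σ², a standard error of about 0.37σ, and the two contrasts correlate at 0.5.

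**Step 3: the two gates.** Let a and c be the estimated anode–sham and cathode–sham contrasts, and s² the residual mean square.

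- Literal gate: F = a² / [(5/36)s²], on 1 and 30 df. The cathodal contrast c does not enter.
- Joint gate: with correlation 0.5, F = (a² − ac + c²) / [2 × 0.75 × (5/36)s²] = (a² − ac + c²) / [(5/24)s²], on 2 and 30 df.

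**Step 4: the plan's own figure.** Under no effects both gates have size 0.050, so the stated α is reproduced on either reading.

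**Step 5: chance of declaring the cathodal effect, literal versus joint gate.** Monte Carlo with 2,000,000 draws per scenario; each gate is followed by the cathode–sham F-test at 0.05. Anodal effects are opposite in sign to the cathodal effect and sized relative to it.

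| Anodal effect | Cathodal 0.5 SD | Cathodal 1.0 SD | Cathodal 1.5 SD |
|---|---|---|---|
| None | 2% vs 18% | 3% vs 68% | 5% vs 97% |
| Half as large | 1% vs 21% | 14% vs 73% | 47% vs 97% |
| Equal | 3% vs 24% | 51% vs 74% | 95% vs 97% |
| 1.5 times as large | 7% vs 25% | 71% vs 74% | 97% vs 97% |

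With no anodal effect the literal gate opens 5% of the time whatever the cathodal effect. For a cathodal effect of 1.0 SD the joint gate opens 75% of the time.

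**Step 6: model without carryover.** Section 11.1 plans sensitivity models with "omission of period effects or sequence effects or carryover effects". Dropping carryover gives v = 1/9 σ² and 54 − 22 = 32 df. For equal and opposite effects of 0.5, 1.0 and 1.5 SD the figures become 5% vs 30%, 67% vs 83% and 98% vs 99%.

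**Step 7: false claims with no true effects.** The chance of rejecting at least one component is 5.0% under the literal gate and 4.2% under the joint gate. If a claim counts when either gate allows it, the chance is 5.0% + 1.7% = 6.7%.

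**The case against.** The strongest reply is that this is a recoverable slip. The printed null is visibly redundant, H_oC is written correctly one sentence later, and most analysts would run the 2-df test. It may even be a fault of text conversion, since one subscript separates right from wrong. The intent is indeed clear, and conversion cannot be excluded, which is why the source file should be checked first. But this is the only statement of the main test, and a silent correction during analysis would be an undocumented change to a plan that presents itself as a priori.

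The second reply is that little hangs on the test. The study is a pilot whose stated focus is estimation: "The fitted model will be used to tabulate statistical estimates (all with 95% confidence intervals) of the parameters of interest", whatever the gate shows. Non-significant tests are to be reported as inconclusive, so a blocked test should not turn into a claim of no cathodal effect. The anode–cathode equivalence test is not gated. All of this stands and limits the harm.

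Third, the effects are assumed, and the widest gaps need no anodal effect, contrary to the study hypothesis. That is fair. Under equal and opposite effects the loss is 2 points at 1.5 SD, and at 0.5 SD the test is weak under either gate. The middle of the range still loses 23 points (74% − 51%).

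Fourth, a correct joint gate can also withhold the cathodal test. At 0.5 SD with no anodal effect, power is 25% ungated and 18% behind the joint gate. True, but the joint gate responds to the cathodal effect and the literal gate does not.

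Fifth, the 6.7% supposes a choice made after seeing the data, which nothing in the documents suggests. It measures what an unresolved ambiguity would permit and does not predict conduct.

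Last, section 2.3.2 also covers TEP amplitudes and a TEP–MEP correlation, so cathode–sham MEP is one part of the hypotheses. It is nonetheless one of the two comparisons that the main test was written to cover.

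**Conclusion.** The main null is wrong as written, and the context leaves little doubt that a joint null was intended. This is an error in the primary decision rule, with limited harm.

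The harm is not type I error, which is controlled under either fixed reading. It is the possible loss of the formal cathode–sham test. That loss is small only when the anodal effect is large, and severe when the anodal effect is absent or clearly smaller than the cathodal one.

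The power figures rest on assumed effects in within-subject SD units, complete data and compound symmetry. The rank of the null, and so the literal gate's indifference to the cathodal contrast, rests on none of these.

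**What to change.** Check the formula against the source file. If it reads as here, correct it by a dated amendment before any data are analysed:

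- Main null: (μA − μS) = 0 = (μC − μS).
- Test: F-test with 2 numerator degrees of freedom at α = 0.05.

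Leave the two gated component tests as they are; with the joint gate, familywise error stays at or below 5%. The cost is one symbol and a statement of the numerator degrees of freedom, with no extra data or participants.

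### No difference test of anode versus cathode is planned; their only direct test is an equivalence test, which would usually be labelled inconclusive when the true difference is 0.1 mV or more

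*Combined protocol and SAP*

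**What the plan says.** Section 2.3.1, Aim 2: "Compare the three tDCS conditions (anode, cathode, sham) in terms of the mean changes in TEP and MEP amplitude".

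Section 2.3.2 gives the directions, each relative to sham: "We hypothesize that anodal and cathodal tDCS stimulation increases and decreases TEP and MEP amplitudes compare to sham tDCS condition, respectively".

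Section 11.1 sets out the tests:

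- An overall F-test at 0.05. As printed, its null names the anode-minus-sham contrast twice: "\mu_A - \mu_S) = 0 = (\mu_A - \mu_S". The sub-hypotheses that follow show that the second term was meant to be cathode minus sham.
- If that test rejects, "then (and only then) we will test the two component sub-hypotheses using F-tests of size" 0.05. The two are anode versus sham and cathode versus sham.
- For anode versus cathode: "We will also perform an equivalence test in which equivalence is defined as a difference of less than" 0.1 mV. The null is non-equivalence, and it is rejected only if the 95% confidence interval for μA − μC lies entirely inside [−0.1, 0.1] mV.
- A reporting rule for every test: "All hypothesis tests that are observed to be NOT statistically significant will be reported as being inconclusive". The next sentence adds that nothing may be concluded from such a test.

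The same paragraph makes point and interval estimates the focus of the analyses.

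**The concern.** An equivalence test has two outcomes: equivalence is concluded, or it is not. It cannot conclude that two conditions differ. The reporting rule suits difference tests, where failure to reject leaves the question open. Applied to a test whose null is non-equivalence, it attaches the word *inconclusive* to results that are clear in the opposite direction, including an interval lying wholly above 0.1 mV. No sentence in Section 11.1 says how such an interval is to be described.

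Two things are at stake. A report could print a confidence interval that excludes zero next to a test labelled inconclusive for the same contrast. And the pairwise contrast with the most power under the hypothesised pattern has no difference test, so the overall test may reject without any planned component explaining why.

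**Working it through.** **Inputs from the documents.** 18 participants, three in each of six sequences, three periods each (Sections 3 and 4.1). Model with treatment, period, sequence and first-order carryover under compound symmetry; T = 0.1 mV; 95% interval; α = 0.05 (Section 11.1).

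**Not in the documents.** No SD, effect size or power is given for this contrast, so there is no planned figure to reproduce. Section 11.2 reports precision only for a proportion, which does not enter here. The within-subject SD (σ) and the effects are assumptions. Dropout is taken as nil.

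**Step 1: standard error.** Least squares on the 54 observations with subject, period, treatment and carryover terms uses 24 parameters, leaving 54 − 24 = 30 df. Every pairwise treatment contrast has variance (5/36)σ² = 0.1389σ², so SE = 0.373σ. With t(0.975, 30) = 2.042, the 95% half-width is 2.042 × 0.373σ = 0.761σ. Equivalence cannot be declared at any observed difference once the estimated σ exceeds 0.1/0.761 = 0.131 mV.

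**Step 2: how often the label applies.** Suppose the true difference is T or more. To declare equivalence, the upper confidence limit must fall below T, and so below the true value. A 95% interval misses on that side with probability 2.5%. The test is therefore non-significant, and labelled inconclusive, with probability at least 97.5% whatever σ is.

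**Step 3: simulated operating characteristics.** Anode and cathode effects are symmetric about sham, and the overall test is taken as the intended 2-df version. Powers for pairwise contrasts are gated: the overall test must also reject.

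| Quantity | ±0.5 SD against sham | ±1 SD against sham |
|---|---|---|
| Overall test rejects | 62% | 99.7% |
| Anode-sham, gated | 24% | 74% |
| Cathode-sham, gated | 24% | 74% |
| Both sham contrasts, gated | 2.7% | 50% |
| Anode-cathode difference, gated (not planned) | 61% | 99.7% |
| Overall rejects, neither sham contrast does | 17% | 2.7% |

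In every simulated trial counted in the last row, the anode-cathode contrast was significant.

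In mV, with assumed σ = 0.2:

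- ±0.5 SD is a true difference of 0.2 mV. The interval excludes zero in 74% of trials and lies wholly above 0.1 mV in 25%.
- ±1 SD is a true difference of 0.4 mV. The interval excludes zero in 99.9% and lies wholly above 0.1 mV in 97%.
- Equivalence is declared in about 0% in both.

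**Step 4: cost in error rate.** With three conditions, any two pairwise equalities imply the third. The only intersection of the pairwise nulls is therefore the overall 2-df null, and testing all three pairs at 0.05 behind it is a closed procedure. Simulated familywise error is 5.0% when all three conditions are equal and about 5% or less when only anode and cathode are equal. This needs the overall null to contain both sham contrasts. As printed it is a 1-df anode-sham test, and closure fails.

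**The case against.** A reader might infer something stronger: that the whole anode-cathode comparison must be reported as inconclusive however large the difference is, so that the trial reaches a wrong conclusion under its own hypothesis. The documents do not support that, for three reasons, and two further points limit the criticism.

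- The rule governs tests. The equivalence criterion itself requires the 95% interval for μA − μC, and Section 11.1 puts the emphasis on estimates. A large difference would be seen. This stands.
- Section 2.3.2 gives directions and no size. Opposite effects totalling less than 0.1 mV fit the hypothesis and can be declared equivalent: at a true difference of 0.05 mV with assumed σ = 0.05 mV, 74% of trials do so. This stands.
- The hypothesis is framed against sham, and the two gated tests match it. Significant sham contrasts in opposite directions would support it indirectly. This stands in part: both are significant in only 2.7% of trials at ±0.5 SD and 50% at ±1 SD, and Aim 2 covers all three conditions.
- An anode-cathode test placed behind the overall F-test detects no additional trials. At ±0.5 SD the overall test already rejects in 62%, against 61% for the gated contrast. True; the gain is in attributing the effect to a pair.
- This is a pilot whose size was set by expert opinion, so an extra test is partly a matter of preference. Fair for the added test, but it does not answer the labelling problem.

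**Conclusion.** The point holds in a limited form. Section 11.1 lists no difference test of anode versus cathode. The one direct test is labelled inconclusive with probability at least 97.5% whenever the true difference is 0.1 mV or more, even if its own interval shows a clear difference. That figure follows from the 95% interval rule and needs no assumed SD, only a valid interval.

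The consequence is a misleading label and a gap in attribution. The estimate itself is not lost. The gap depends on the assumed effect: in 17% of trials at ±0.5 SD, and 2.7% at ±1 SD, the overall test rejects with neither planned component significant. These shares assume symmetric opposite effects, complete data, the Section 11.1 model and the overall null as evidently intended. It should be put right before analysis, but it does not undermine the trial's estimation aims.

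**What to change.** In Section 11.1:

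1. Correct the overall null to (μA − μS) = 0 = (μC − μS), so that it is a 2-df test.
2. Add a third component hypothesis, μA − μC = 0, tested at α = 0.05 only if the overall null is rejected. State that the three pairwise tests form a closed procedure and need no further adjustment.
3. Keep the equivalence test as secondary, and state that a 95% interval for μA − μC lying wholly outside [−T, T] is reported as a difference larger than T. Reserve *inconclusive* for an equivalence result whose interval straddles −T or T.

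The cost is a few sentences. No participants, measurements or alpha are added, and the interval needed is already being computed.
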